## 7. STATISTICAL ANALYSIS

## 7.1 Sample Size

Since this is a pilot study, the estimate of sample size to determine a biologic signal in patients with LAM is extrapolated from other studies in which serial samples of VEGF-D has been measured. Since LAM is a rare disease a small trial is designed to assure enrollment is achievable. This study will enable proper powering of subsequent studies. The authors believe that a proof of principal pilot study will be able to recruit 20 participants, the majority on rapamycin, for this study. A larger study is not possible given the limitations of funding.

## 7.2 Statistics

Statistical analysis of the primary endpoint will compare the VEGF-D before and one month after imatinib montherapy by intrasubject testing. VEGF-D has been shown to be logarithmically expressed and log transformation of the data is planned. It is unlikely that data will be normal between the imatinib and placebo groups. Therefore, the intrasubject difference (log pg/ml) in VEGF-D between imatinib and placebo groups will be subjected to non-parametric analysis with Wilcoxen rank sum tests. All statistical tests will be 2-sided at a 0.05 level of significance.

Statistical analysis of secondary endpoints will be performed in identical manner using the % change in FEV1 and FVC for these analyses. Use of ml change disproportionately shows effects in this bronchodilator responsive disease for those with preserved lung function. All secondary endpoints will be reported in study manuscripts with adjustment for multiplicity testing. Data will be presented in spaghetti plots to allow an assessment for responder analysis.

Exploratory analyses are designed to not miss a biologic signal if present. The impact of any significant difference between groups will require additional study and will be presented as question generating and will not use adjustments for multiplicity testing.

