## 5. STUDY DESIGN AND PROCEDURES

## 5.1 Overview

The proposed study design is a prospective, multicenter, randomized, stratified, double blind, placebocontrolled, proof of principal trial to examine the effect of imatinib mesylate on intrasubject VEGF-D, a biomarker associated with LAM disease activity.

The study is designed as a 3 visit study including baseline, 1 month, and 2 month visits. Since most patients with impaired lung function who would be eligible for this study are already on sirolimus, the proposed study would simultaneously address three issues: 1) provide a biomarker rich proof of principle study of imatinib mesylate in LAM, 2) determine if imatinib mesylate is safe when added to sirolimus, and 3) determine if imatinib mesylate controls vascular endothelial growth factor-D (VEGF-D) once sirolimus is removed. Small numbers of individuals are not on sirolimus; however, this proposal would not exclude them to define if there is a treatment response signal to imatinib mesylate alone. A stratified randomization strategy will differentially enroll participants on or off rapamycin at baseline.

At the conclusion of the study, participants will be returned to clinically available LAM therapy chosen with their treating physician. Imatinib will not be available through the investigators after participation in this study.

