## 5.4 Visit Schedule

**The Baseline Visit** will begin with signing the informed consent. A history and physical examination, post-bronchodilator spirometry, 6 minute walk test distance, and blood samples will be obtained. Questionnaires will be completed and the patient will be randomized to imatinib mesylate, at an oral dose of 400 mg once daily, or placebo stratified on whether sirolimus has been used in the last month. A sirolimus level and VEGF-D level will be measured.

A 1 week trough sirolimus level and telephone call will be obtained on all subjects entering the study on sirolimus therapy.

**1 Month Visit-** Post-bronchodilator spirometry, 6 minute walk test distance, and blood samples will be obtained. Questionnaires will be completed. Sirolimus will be discontinued if used at baseline.

**2 Month Visit/ End of study-** Post-bronchodilator spirometry, 6 minute walk test distance, and blood samples will be obtained. Questionnaires will be completed. A sirolimus level will be obtained to assure drug cessation. The participant is returned to LAM therapy of their choice.

[figure not shown]

Figure 1. Study Schedule, Stratification and Randomization

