## \*Table 2. Sample Collection and Usage

Collection	Volume	Sample	Time(s)*	Planned assays
Blood each visit	30ml	Plasma	0, 1, 2	Cholesterol, CMP
				Sirolimus level, TSH,
				T4, VEGF-D level
	7 ml	Plasma	1 week in patients on	Sirolimus level
			sirolimus at baseline	
	5ml	EDTA	0, 1, 2	CBC
	10ml	Paxgene DNA	0	DNA
	10ml	Paxgene RNA	0, 2	Blood mononuclear cell
				RNA
Urine each visit	10ml	Urine	0, 1, 2	Urinalysis, Pregnancy
				Test

\*Time 0= Baseline, 1=1month, 2=2 months

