## 7.3 Endpoints

**7.3.1 The primary efficacy analysis** will be the log transformed change in intrasubject plasma VEGF-D before and 1 month after initiation of monotherapy imatinib mesylate. Log transformation was needed in the MILES study because this serum concentration can often go quite high in some patients. VEGF-D will be obtained at baseline and at 28 and 56 days after initiation of imatinib. Note that this analysis will allow the use of sirolimus using and sirolimus naïve participants.

**7.3.2 Secondary endpoints** are obtained to test both efficacy and inform about quality of life. Quality of life questionnaire instruments are described in a later attachment as guided by the CDMRP program. Importantly, respiratory specific and general quality of life scores will be used in the study. Recently, the St Georges Respiratory Questionnaire (SGRQ) was retrospectively validated against four anchors in the MILES study and will be used as a secondary efficacy endpoint in the combined analysis of both stratified randomization populations. To minimize multiplicative analysis, 3 endpoints are chosen for combined population secondary endpoints: Intrasubject Change in FEV1 (ml), Intrasubject Change in FVC (ml), and Intrasubject Change in SGRQ (points) between the timepoints of Baseline and 1 month after initiation of monotherapy imatinib/placebo. The last secondary endpoint compares a 2 month treatment with imatinib/placebo in sirolimus naive participants on intrasubject change in log VEGF-D (pg/ml).

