## 7.3.3 Exploratory endpoints

The table below lists the exploratory endpoints that will be collected to define if there is a difference between the 4 populations in the study. All change variables are measured intrasubject.

Efficacy Endpoints	Difference in baseline and 1 month after initiation of monotherapy imatinib/placebo	Difference in baseline and 1 month in patients on sirolimus	Difference in baseline and 2 months in imatinb naive participants
Change in VEGF-D (log pg/ml)	X (Primary)	X (Exploratory)	X (Secondary)
Change in FVC (%)	X (Secondary)	X (Exploratory)	X (Exploratory)
Change in FEV1 (%)	X (Secondary)	X (Exploratory)	X (Exploratory)
Change in mMRC Dyspnea (score)	X (Exploratory)	X (Exploratory)	X (Exploratory)
Change in 6MWT distance (M)	X (Exploratory)	X (Exploratory)	X (Exploratory)
EQ-5D (score)	X (Exploratory)	X (Exploratory)	X (Exploratory)
Functional Assessment	X (Exploratory)	X (Exploratory)	X (Exploratory)

Inventory (score)			
SGRQ (score)	X (Secondary)	X (Exploratory)	X (Exploratory)

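### The start day of the primary VEGF-D change is ambiguous for sirolimus users, and the two readings estimate different quantities

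*Combined protocol and SAP*

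**What the plan says.** Section 7.2 defines the primary comparison this way: "Statistical analysis of the primary endpoint will compare the VEGF-D before and one month after imatinib montherapy by intrasubject testing". Sections 3.1 and 7.3.1 both describe the "log transformed change in intrasubject plasma VEGF-D before and 1 month after initiation of monotherapy imatinib mesylate". None of the three names a day for the start value.

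The table in 7.3.3 heads the column marked Primary for VEGF-D as "Difference in baseline and 1 month after initiation of monotherapy imatinib/placebo". The footnote to Table 2 fixes the term: "Time 0= Baseline, 1=1month, 2=2 months". Section 7.3.2 also uses baseline as the start of the FEV1, FVC and SGRQ secondary endpoints, which 7.2 says are analysed in the same way as the primary.

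On timing, 7.3.1 says "VEGF-D will be obtained at baseline and at 28 and 56 days after initiation of imatinib". Study drug begins at the baseline visit. At the 1 month visit, according to 5.4, "Sirolimus will be discontinued if used at baseline". Participants not on sirolimus are included to "define if there is a treatment response signal to imatinib mesylate alone", so they are on study drug alone from Day 0. Section 7.3.2 makes their 2 month VEGF-D change a separate secondary endpoint. Section 7.3.1 places both groups in the primary analysis. The test in 7.2 is a two-sided rank-sum test at 0.05 with no stratification stated, although 5.4 stratifies randomisation on sirolimus use in the last month.

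**The concern.** In a sirolimus user, study drug starts at Day 0 and monotherapy starts at Day 28. A change measured from before monotherapy is naturally read as starting from the Day 28 sample. Two other parts of the protocol encourage that reading: the rationale in 2.2 that sirolimus may have to be removed before imatinib's effect shows, and the second aim in 3.2 on one month of withdrawal. That aim needs the Day 28 to 56 change, which no column of the 7.3.3 table supplies.

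The Day 28 value is taken after randomisation, when the imatinib arm has already had a month of imatinib added to sirolimus. Section 6.1.3 notes a known interaction that raises sirolimus levels in that month, so Day 28 VEGF-D could differ between arms. Starting there subtracts that difference from the primary result.

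The trial is meant to supply the effect estimate for designing a phase 3 study, and an estimate with an unsettled start day serves that purpose poorly. If the day is settled after unblinding, the primary result could be chosen from two candidates.

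**Working it through.** **Plan's own figure.** The sample size of 20 cannot be reproduced, because 7.1 gives no effect size, SD or power. For scale only, with 10 per arm, two-sided 0.05 and 80% power, the normal approximation gives a detectable difference of (1.960 + 0.842) × √(2/10) = 1.25 SD.

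**Step 1: windows implied by the visit schedule.**

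| Stratum | Monotherapy starts | One month later | Start read as baseline | Start read as just before monotherapy |
|---|---|---|---|---|
| Users | Day 28 | Day 56 | Day 0 to 56 | Day 28 to 56 |
| Non-users | Day 0 | Day 28 | Day 0 to 28 | Day 0 to 28 |

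The readings differ only in users. Under either one, users' changes ending at Day 56 are ranked together with non-users' Day 0 to 28 changes.

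**Step 2: what each reading estimates in users.** Let E28 and E56 be the imatinib-minus-placebo differences in mean log VEGF-D at those days. At Day 0 the expected difference is zero by randomisation.

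- Day 0 start: E56.
- Day 28 start: E56 - E28.

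This needs no assumed values.

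**Step 3: size under assumed values.** From the documents: 10 sets of each treatment (section 6), the rank-sum test and alpha (7.2), and mostly sirolimus users (7.1). Assumed: 8 users and 2 non-users per arm; independent monthly increments with SD 0.3 log; imatinib effect a in month 1 and b in month 2, equal in both strata, with a + b = -0.4; no rise on sirolimus withdrawal.

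Pooled mean arm difference:

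- Day 0 start: 0.8(a + b) + 0.2a
- Day 28 start: 0.8b + 0.2a

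For a = -0.4 and b = 0, these are -0.32 - 0.08 = -0.40 and 0 - 0.08 = -0.08. For a = b = -0.2, they are -0.32 - 0.04 = -0.36 and -0.16 - 0.04 = -0.20. For a = 0 and b = -0.4, both are -0.32.

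Rejection rates come from 20,000 simulated trials per cell, with exact critical values U ≤ 23 or U ≥ 77. The last two columns add a withdrawal rise of 0.5 log in all users.

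| Effect arises | Difference, Day 0 / Day 28 | Rejection, Day 0 | Rejection, Day 28 | Day 0, rise 0.5 | Day 28, rise 0.5 |
|---|---|---|---|---|---|
| In the add-on month | -0.40 / -0.08 | 51.0% | 5.4% | 39.9% | 1.4% |
| Equally in both months | -0.36 / -0.20 | 41.2% | 25.7% | 34.9% | 15.2% |
| Only after withdrawal | -0.32 / -0.32 | 30.7% | 51.5% | 28.6% | 48.2% |
| No effect | 0 / 0 | 4.4% | 4.4% | 2.0% | 1.7% |

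With 9 users per arm and no rise, the add-on-month row is 49.7% against 4.2% and the after-withdrawal row is 38.8% against 64.7%. With 7 users they are 54.0% against 8.2% and 24.1% against 38.8%.

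**Step 4: sensitivity to the noise model.** The Day 28 advantage in the third row arises because monthly noise accumulates: the SD is 0.3 × √2 = 0.42 over Day 0 to 56, against 0.3 over Day 28 to 56. A second assumed model has 9 against 9 users only, independent noise of SD 0.35 log at each visit, a placebo rise of 0.5 and an effect of 0.6 at Day 56. It gives about 61% power from Day 0 whatever share f of the effect is present at Day 28. From Day 28, power is about 61%, 38%, 20%, 7% and 4% for f = 0, 0.25, 0.5, 0.75 and 1. Under that model the Day 28 start is never better.

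**Step 5: the pooled ranking.** A 0.5 withdrawal rise separates users' changes from non-users'. The unstratified test then becomes conservative (4.4% falls to 2.0% from Day 0) and loses power (51.0% falls to 39.9% in the first row). The cost of pooling is power, not false positives.

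**The case against.** The strongest reply is that the plan nearly settles the matter itself. A reader might infer that two sections name conflicting days. They do not: no section gives Day 28 as the start, and *before* is satisfied by a Day 0 sample. Every explicit start point, in 7.3.2 and 7.3.3, is baseline. This stands, and it makes the defect an ambiguity beside explicit labels. It does not close the gap, because three sections that define the primary, including the one specifying the test, use wording whose natural meaning in users is Day 28. The schedule figure in 5.4 was not available in the text reviewed and might bear on this.

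A second reply is that pooling is deliberate and aligns both strata at one month of monotherapy. That also stands. A reader might infer that the non-users' Day 56 value is lost, but it is a named secondary endpoint. Stratified randomisation should keep the mix of windows roughly balanced between arms. What remains is that the test ignores the stratification factor.

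Third, under the rationale in 2.2 the effect may appear mainly after withdrawal, and the readings then estimate the same quantity. A reader might infer that a Day 28 start always costs power; the third row of the table shows otherwise. It is fair to add that this is a small, funding-limited pilot with individual data plotted, so both windows can be shown. That helps interpretation but does not say which one is primary.

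**Conclusion.** The point holds as an ambiguity in the primary endpoint that changes what is estimated in most participants. It should be resolved before unblinding. That a Day 28 start gives E56 - E28 follows from the schedule alone. The sizes rest on assumed SD, effect, timing and stratum mix: in the base case the arm difference ranges from identical under both readings (-0.32) to five-fold different (-0.40 against -0.08), with power favouring Day 0 in some settings and Day 28 in others.

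Two stronger conclusions are not supported. Type I error is not inflated for either window fixed in advance (at most about 4% here); the risk lies in choosing between them after seeing the data. A reversal of sign is possible algebraically, but only if E28 exceeds E56 in the same direction, that is, if a month 1 effect fades by Day 56. The documents give no figures to show that this would happen.

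**What to change.** In 3.1, 7.2 and 7.3.1, state that the primary change starts at Day 0 (the randomisation visit) for every participant, matching 7.3.2 and 7.3.3. State that it ends one month after monotherapy starts: Day 56 in sirolimus users and Day 28 in non-users. In 7.2, stratify the rank-sum test by baseline sirolimus use, which is already a randomisation factor. Name the Day 28 to 56 change in users as a supportive analysis serving the withdrawal aim in 3.2, and note that it starts from a post-randomisation value.

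The cost is wording in three sections; all three VEGF-D samples are already planned. The downside is some loss of power if the imatinib effect appears only after withdrawal (30.7% against 51.5% in the base case, none under the per-visit noise model). Moving non-users to Day 56 is optional and not part of this fix. It would equalise time on randomised drug, but it would give up the alignment at one month of monotherapy and duplicate their existing secondary endpoint.

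### The primary rank-sum test leaves out the sirolimus stratum and handles baseline log VEGF-D only by subtraction; it is valid, but can lose power and is sensitive to chance baseline imbalance

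*Combined protocol and SAP*

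**What the plan says.** Section 7.3.1 defines the primary endpoint as "the log transformed change in intrasubject plasma VEGF-D before and 1 month after initiation of monotherapy imatinib mesylate". Section 7.2 sets the scale ("VEGF-D has been shown to be logarithmically expressed and log transformation of the data is planned"), the reason for a rank method ("It is unlikely that data will be normal between the imatinib and placebo groups"), the test ("the intrasubject difference (log pg/ml) in VEGF-D between imatinib and placebo groups will be subjected to non-parametric analysis with Wilcoxen rank sum tests") and the level ("All statistical tests will be 2-sided at a 0.05 level of significance").

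The two variables at issue are available for everyone. In 7.3.1, "VEGF-D will be obtained at baseline and at 28 and 56 days after initiation of imatinib". In 5.4, randomisation is "stratified on whether sirolimus has been used in the last month". Under the same section, participants who entered on sirolimus stop it at the 1 month visit.

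Section 7.1 expects that the study "will be able to recruit 20 participants, the majority on rapamycin, for this study". It gives no effect size, SD or power. Section 6 describes 10 imatinib and 10 placebo sets, with 5 sets of each label sent to the second site. No section adds a stratum or baseline term to the primary test, and 7.2 has the secondary endpoints follow the same method.

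**The concern.** Two pieces of information that the trial collects do not enter the primary test.

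The first is the stratum. Between baseline and follow-up, sirolimus users come off a drug that the Introduction says lowers VEGF-D, and the other participants do not. If users' VEGF-D rises as a result, the two strata have different typical changes. Stratified allocation balances that difference between arms. An unstratified test still counts it as noise, so it becomes too conservative and loses power.

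The second is baseline. A change score assumes that each unit of log baseline carries through in full to follow-up. If the true slope is below 1, participants who start high tend to fall whatever they receive. An arm that starts higher by chance then appears to respond better. With 10 per arm, such imbalance is likely.

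The plan says a larger study is not possible, so efficiency has to come from the analysis.

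**Working it through.** **Inputs from the documents.** N = 20, 10 per arm; two-sided 0.05; rank-sum test on change in log VEGF-D; randomisation stratified on sirolimus. There is no planned power figure to reproduce.

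**Assumed, because the documents are silent.** Effect 1.325 SD of change, which gives about 80% power for a t-test with 10 per arm (the normal approximation gives 80% at (1.960 + 0.842) × √(2/10) = 1.25 SD). Correlation rho between baseline and follow-up 0.5 to 0.95. 16 or 18 of 20 on sirolimus. Normal log values and no dropout.

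**Step 1: stratum.** Let a fraction p be on sirolimus and let the strata differ by k SD of change. The within-arm variance that the test sees is 1 + k²p(1−p). The true standard error of the arm difference stays at √(2/10) = 0.447, because allocation balances the strata. Approximate t-test power is Φ(1.325/0.447 − 2.101 × √(1 + k²p(1−p))), where 1.325/0.447 = 2.963. At p = 0.8:

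| Stratum shift | Variance seen | Approximate t-test power | Simulated t-test | Simulated planned rank-sum |
|---|---|---|---|---|
| 0 | 1.00 | Φ(0.862) = 0.81 | 0.80 | 0.76 |
| 1 SD | 1.16 | Φ(0.700) = 0.76 | 0.75 | 0.70 |
| 2 SD | 1.64 | Φ(0.272) = 0.61 | 0.59 | 0.55 |

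Across 16 to 18 on sirolimus and the correlations tried, planned power is about 75%, 69-74% and 52-68% for shifts of 0, 1 and 2 SD. At 2 SD with 16 on sirolimus, the planned test's type I error falls to about 1.3-1.6%. Adjusting for stratum alone brings power to about 72-78%.

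**Step 2: baseline, equal SDs.** Variance of change is 2s²(1−rho); variance after baseline adjustment is s²(1−rho²). The ratio is (1+rho)/2, times about 1 + 1/(20−4) = 1.0625 for estimating the slope.

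| rho | (1+rho)/2 | With slope cost | t-test on change | ANCOVA |
|---|---|---|---|---|
| 0.5 | 0.75 | 0.80 | 0.80 | 0.88 |
| 0.7 | 0.85 | 0.90 | 0.80 | 0.84 |
| 0.8 | 0.90 | 0.96 | 0.81 | 0.82 |
| 0.9 | 0.95 | 1.01 | 0.80 | 0.79 |

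The last two columns are simulated power (20,000 trials per setting). They isolate baseline adjustment from the choice between rank and parametric tests.

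**Step 3: baseline, unequal SDs.** With r = follow-up SD / baseline SD, the best slope is rho × r, and the variance ratio is r²(1−rho²) / (1 + r² − 2·rho·r).
- rho 0.7, r 1.2: slope 0.84; 0.734/0.760 = 0.97, or 1.03 with the slope cost.
- rho 0.8, r 1.25: slope 1.00; 0.5625/0.5625 = 1.00, or 1.06 with the slope cost.

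A modest growth in spread therefore removes the gain.

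**Step 4: chance imbalance.** The standard error of the baseline arm difference is 0.447 baseline SD. With equal SDs, change carries (1−rho) of the imbalance into the effect. Simulated power of the planned test when imatinib starts more than 1 SE higher, against more than 1 SE lower:
- rho 0.5: 0.94 against 0.51
- rho 0.7: 0.89 against 0.57
- rho 0.9: 0.84 against 0.66

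ANCOVA gives 0.86 against 0.86, 0.80 against 0.82, and 0.76 against 0.76. Averaged over imbalance and with no stratum shift, the planned test's type I error is 0.041-0.045.

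**Step 5: the proposed rank test.** With log baseline and stratum both in the model and equal SDs, power is about 83-85% at rho 0.5 and 78-80% at rho 0.7. With no stratum shift, the gain from baseline is 6-8 points at rho 0.5, 2-3 at 0.7 and none at 0.9. There is a loss of about 2-4 points if the follow-up SD is 1.2-1.25 times baseline.

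**The case against.** The planned test is pre-specified, simple and valid, and this is a feasibility-sized pilot. It already removes the stable differences between people by subtraction. Users stop sirolimus between the two measurements, so equal spread at baseline and follow-up cannot be presumed. If spread grows by 1/rho, the change score is already optimal. All of this stands.

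Three stronger readings are tempting, and the documents do not support them.
- A reader might infer that the test ignores baseline or uses raw values. It does neither: the outcome is a log-scale change, so baseline enters with slope 1.
- A reader might infer that the test is invalid or inflates false positives. Overall type I error is at or below 5%. The imbalance problem is conditional on the baseline difference that happens to occur.
- A reader might infer that baseline adjustment is sure to gain power. That depends on a correlation and an SD ratio that the documents do not give.

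The objection does not answer the stratum omission. A 2 SD shift at rho 0.7 with 16 on sirolimus shows which term matters more: power is 0.55 as planned, 0.61 for ANCOVA with baseline only, and 0.84 for ANCOVA with baseline and stratum.

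**Conclusion.** The point holds as a matter of efficiency and robustness, not validity. The stratum is the dependable part. Adjusting for it costs almost nothing if the strata behave alike; if they differ by 2 SD of change, it lifts power from 52-68% to about 72-78%. The documents make a difference plausible but do not establish one, and 7.4 says the time for LAM cells to regrow off sirolimus is unknown.

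The baseline part is conditional. It is worth having at correlations of about 0.5 to 0.7 with similar SDs, and worth little or slightly harmful at 0.9 or with wider follow-up spread. Its steadier benefit is that the result depends less on which arm happened to start higher.

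All sizes rest on the assumed effect of 1.325 SD of change, 16-18 of 20 on sirolimus, normal log values and full follow-up.

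**What to change.** In 7.2, before unblinding, make the primary test a stratified, baseline-adjusted rank test:
1. Regress the primary follow-up log VEGF-D on log baseline and sirolimus stratum, with arm omitted.
2. Compare the residuals between arms with the rank-sum statistic.
3. Take the p-value by re-randomising arm according to the allocation scheme actually used: within stratum, and within site if allocation was restricted by site, as the 5 and 5 shipment in Section 6 suggests.
4. Report the adjusted geometric mean ratio (imatinib/placebo) with a 95% CI, noting that this interval leans on approximate normality of log residuals while the p-value does not.
5. Keep the unadjusted rank-sum test on change as a sensitivity analysis.

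State the follow-up visit for each stratum as 7.3.1 defines it. For sirolimus-naive participants, one month of monotherapy can be read as day 28, and their 2 month change is already a separate secondary endpoint, so day 56 should not be imposed on everyone by default.

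Form the residuals on the log scale and then rank them. Regressing ranks on ranks (Quade) is a different method, and its power fell to 0.73 at rho 0.8 and 0.66 at rho 0.9.

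The cost is a few sentences, a few lines of code and no new data. It spends one or two degrees of freedom, and a few points of power if the best slope is near 1 and the strata do not differ.

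### Randomisation is stratified by sirolimus use, but the pooled primary rank-sum test in 7.2 ignores the stratum, which can cost power if sirolimus withdrawal raises VEGF-D

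*Combined protocol and SAP*

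**What the plan says.** Section 5.1 announces the stratification: "A stratified randomization strategy will differentially enroll participants on or off rapamycin at baseline". Section 5.4 randomises to imatinib "or placebo stratified on whether sirolimus has been used in the last month", and its 1 month visit adds "Sirolimus will be discontinued if used at baseline".

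Section 7.2 describes the primary analysis twice. It "will compare the VEGF-D before and one month after imatinib montherapy by intrasubject testing", and then the intrasubject "difference (log pg/ml) in VEGF-D between imatinib and placebo groups will be subjected to non-parametric analysis with Wilcoxen rank sum tests", two-sided at 0.05. Neither sentence mentions a stratum, a stratified test or an exact version.

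Section 7.3.1 pools the two groups: "Note that this analysis will allow the use of sirolimus using" and sirolimus-naive participants alike. The table in 7.3.3 gives the interval for the primary endpoint as "Difference in baseline and 1 month after initiation of monotherapy imatinib/placebo". Section 7.3.2 keeps a longer interval for a separate secondary endpoint: "The last secondary endpoint compares a 2 month treatment with imatinib/placebo in sirolimus naive participants".

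**The concern.** Sirolimus is withdrawn partway through the study in one stratum and not in the other. The documents support a rise in VEGF-D as the likely direction. Section 1 says sirolimus lowers VEGF-D, section 2.1 describes rapid loss of lung function when it was stopped in the cited earlier trial, and Aim 2 asks about elevation after withdrawal. They give neither the size nor the timing of a rise, and 7.4 calls the regrowth interval unknown.

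If there is a rise, users and non-users have different expected changes whatever imatinib does. A pooled rank test treats that difference as noise. With 20 participants and one primary test, the loss could matter, and the randomisation already records the factor needed to avoid it. If the few non-users fall mostly in one arm, the pooled result also depends partly on which arm that is.

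**Working it through.** **Time points.** Monotherapy starts at month 1 for users and, by inference, at Day 0 for non-users. On the 7.3.3 heading, the change runs Day 0 to 56 for users and Day 0 to 28 for non-users. If *before* in 7.2 means the start of monotherapy, the users' change runs Day 28 to 56. Withdrawal falls inside the users' interval on either reading.

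**The plan's own figure.** N = 20 (sections 5.2 and 7.1) comes without an effect, SD or power, so it cannot be reproduced. For scale, a normal approximation with 10 per arm and a 1.25 SD effect gives Φ(1.25 × √(10/2) − 1.96) = Φ(0.835) = 79.8%.

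**Inputs from the documents.**
- Two-sided 0.05 (7.2).
- 10 v 10, with five sets of each label for one site's 10 participants (section 6).
- 90% of patients with low lung function on sirolimus (section 6), which gives 18 users and 2 non-users if it carries over.

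**Assumed inputs.** Normal log changes with SD 0.3, imatinib effect −0.4 (0.4/0.3 = 1.33 SD) in both strata, withdrawal rise *d* from 0 to 0.7 (0 to 2.33 SD), and all 20 completing.

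**Model.** Mean change is *d* (users, placebo), *d* − 0.4 (users, imatinib), 0 (non-users, placebo) and −0.4 (non-users, imatinib).

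**Tests.** The pooled test uses the rank sum over all 20. The stratified (van Elteren) test uses Σ W_h/(N_h + 1), with ranks taken within stratum. Both use exact null distributions, with 40,000 simulated trials per cell (Monte Carlo SE about 0.2 points).

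**Rough check.** The pooled variance is about 0.3² + p(1 − p)*d*², where p is the share of users. At *d* = 0.7:
- 18/2: 0.09 + 0.09 × 0.49 = 0.134, so the SD is 0.366 and the effect is 0.4/0.366 = 1.09 SD.
- 16/4: 0.09 + 0.16 × 0.49 = 0.168, so the SD is 0.410 and the effect is 0.4/0.410 = 0.97 SD.

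The within-stratum effect stays at 1.33 SD.

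**Power, %, pooled v stratified:**

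| Users/non-users, allocation | d = 0 | 0.2 | 0.4 | 0.7 |
|---|---|---|---|---|
| 18/2, one non-user per arm | 76 v 76 | 75 v 76 | 71 v 76 | 64 v 76 |
| 16/4, two non-users per arm | 76 v 76 | 73 v 75 | 66 v 76 | 50 v 76 |
| 18/2, both non-users on imatinib | 76 v 70 | – | – | 88 v 71 |
| 18/2, both non-users on placebo | 76 v 70 | – | – | 29 v 70 |
| 18/2, averaged over allocations | 76 v 73 | 74 v 73 | 70 v 73 | 61 v 73 |

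The last row gives half the weight to one-arm allocations; at 0.7 the pooled figure is 0.5 × 64 + 0.25 × 88 + 0.25 × 29 ≈ 61. Without blocking within stratum, two non-users share an arm with probability 4/9 if both are at one site with 5 + 5 sets, or 1/2 if there is one per site. Break-even lies between a rise of 0.25 (73.5 v 73.2) and 0.3 (72.1 v 73.0).

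**Other cases.**
- 19/1: 75.9 v 73.3 with no rise, 73.6 v 73.5 at 0.35, 68.4 v 73.6 at 0.7.
- 18/2 with one non-user lost: 73.6 v 69.5 with no rise, 70.1 v 69.6 at 0.4, 65.5 v 69.4 at 0.7.
- Imatinib fully cancels the rise in users and does nothing in non-users (close to the equivalence hypothesis in 2.3), balanced strata, rises 0.2, 0.4, 0.7: 21 v 23, 64 v 68, 98 v 99 at 18/2; 17 v 19, 51 v 55, 92 v 93 at 16/4. Part of this gain is discreteness (attained alpha 4.3% pooled, 4.8 to 4.9% stratified).
- Effect of 1.0 to 1.67 SD, 18/2 averaged: a cost of 2 to 3 points with no rise, a gain of 2 to 3 at a 1.33 SD rise and 10 to 12 at 2.33 SD.
- Heavier tails (t with 3 df, effect 1.35 SD, 16/4 balanced): 55.6 v 55.9 with no rise, 39.1 v 55.3 at a 2 SD rise.

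**Type I error of the pooled test, 18/2.** Balanced, it is 3.1% at a rise of 0.4 and 2.1% at 0.7. With both non-users in one arm, it is 5.6% and 6.6 to 6.7%. Averaged over allocations, it is 4.1 to 4.5%. The stratified test stays between 4.2 and 5.1% throughout.

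**The case against.** The pooled test is valid on average, and at 18/2, the only split the documents suggest, the benefit is uncertain. Without blocking, stratifying loses power for rises below roughly 0.25 to 0.3, close to 1 SD, and no section gives the size of a rise. When both non-users share an arm, the stratified test ignores them, although 5.1 keeps them in order to look for a response to imatinib alone. The separate analyses in 7.3.3 and the spaghetti plots already show the strata apart.

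Much of this stands. The sign of the trade-off depends on the rise and on blocking that the documents do not describe. Under full cancellation the result is also mixed. The averaged gain at a rise of 0.4 is 69.2 − 63.9 = 5.3 points, but with both non-users on imatinib the comparison is 75.9 v 70.5 against stratifying.

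Two simplifications remain. The same effect and SD are used for both strata despite different exposure times, and everyone is assumed to complete although 6.4 ends participation on a 10% FEV1 or FVC decline.

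Three things do not follow. Separate exploratory analyses do not change the primary test. The pooled test's 88% when both non-users are on imatinib reflects an imbalance that favours imatinib, not better evidence. The 90% share describes patients with low lung function, while 5.3.1 admits FEV1 or FVC up to 90% predicted. More non-users than two are therefore possible, and at 16/4 the pooled test loses more.

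**Conclusion.** The concern holds as a cheap improvement. The omission in 7.2 is plain on the text; the size of the benefit is conditional. With balanced strata, stratifying costs essentially nothing at 18/2 or 16/4 when there is no rise. At a rise of 0.7 it recovers about 12 points (18/2) to 26 points (16/4). Averaged over unblocked allocations at 18/2, it costs about 3 points with no rise and gains about 12 at 0.7. If imatinib fully cancels the rise, the gain is small with balanced strata and can be negative in one allocation.

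These figures rest on the assumed SD, effect, rise, split and full completion. The pooled test does not inflate type I error averaged over allocations. The case for the stratified test is that it follows the randomisation and keeps its error rate and power from depending heavily on where a handful of non-users land.

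**What to change.** - **7.2:** name the exact stratified (van Elteren) rank-sum test, by randomised sirolimus stratum, for the primary endpoint and the combined-population secondary endpoints. State that a stratum with all its participants in one arm contributes nothing to the test.
- **7.3.1:** write out the time points for each stratum. The 7.3.3 table points to Day 0 to 56 for users and Day 0 to 28 for non-users; correct this if another reading is meant.
- **Aim 2:** if *before* is Day 0 for users, no listed endpoint isolates the change after withdrawal. In that case also report the Day 28 to 56 change in log VEGF-D in the imatinib arm of the sirolimus stratum.

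The cost is SAP wording, settled before unblinding, and a standard procedure. No samples or participants are added, because VEGF-D is already measured at all three visits. The price in power if there is no rise is nil with balanced strata at 18/2, about 6 points if both of two non-users share an arm, about 3 points averaged without blocking, 2 to 3 points at 19/1, and about 4 points if one of two non-users is lost. Stating the blocking within strata would show which of these applies.
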